11.0 SUBJECT DATA PROTECTION

In accordance with the Health Information Portability and Accountability Act (HIPAA), a subject must sign an authorization to release medical information to the sponsor and/or allow the sponsor, a regulatory authority, or Institutional Review Board access to subject's medical information that includes all hospital records relevant to the study, including subjects' medical history.

12.0 RETENTION OF RECORDS

The Principal Investigator of The Case Comprehensive Cancer Center supervises the retention of all documentation of adverse events, records of study drug receipt and dispensation, and all IRB correspondence for as long as needed to comply with local, national and international regulations. No records will be destroyed until the Principal Investigator confirms destruction is permitted.

13.0 AUDITS AND INSPECTIONS

Authorized representatives of the sponsor, a regulatory authority, an Independent Ethics Committee (IEC) or an Institutional Review Board (IRB) may visit the site to perform audits or inspections, including source data verification. The purpose of an audit or inspection is to systematically and independently examine all study-related activities and documents to determine whether these activities were conducted, and data were recorded, analysed, and accurately reported according to the protocol, Good Clinical Practice (GCP), guidelines of the International Conference on Harmonization (ICH), and any applicable regulatory requirements. For multi-center studies, participating sites must inform the sponsor-investigator of pending audits.

14.0 STATISTICAL CONSIDERATIONS

The primary objective of the study is to measure the frequency with which DBT alters the surgical plan. For this objective, the proportion of subjects with a change in surgical plan will be calculated and its 95% Confidence Interval (CI) constructed. Logistic regression models will be used to identify variables on 2D that are predictive of patients who would benefit from DBT.

The dependent variable in the models will be change/no change in surgical plan, and the independent variables will be lesion and breast characteristics. Holm's method will be used to control the family-wise type I error rate. McNemar's test will be used to compare the findings on MRI and DBT.

Sample Size Justification:

A 95% CI for the proportion of patients with changes in their surgical plan attributable to DBT can be constructed with width of +/- 8% or tighter with 150 patients.

REFERENCES

3. Skaane P, Bandos AI, Gullien R, et al. Prospective trial comparing full-field digital mammography (FFDM) versus combined FFDM and tomosynthesis in a

population-based screening programme using independent double reading with arbitration. *Eur Radiol* 2013;23(8):2061–2071.

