1.0 Introduction

1.1 Background / Rationale

Currently, only MRI is occasionally used to evaluate the extent of disease in some cancer patients, based on age, breast density and pathology subtype of the breast cancer. It is a sensitive, but relatively expensive, time consuming test given the additional work up (second look ultrasounds and biopsies) required for findings noted on the MRI. This adds to both the diagnosis cost and time to treat. It also helps in assessing chemotherapy response and surgical treatment planning.

Our goal is to evaluate the efficacy of DBT in a similar fashion to study its role in cancer extent evaluation, finding additional ipsilateral and contralateral cancers, assess for multicentric and multifocal disease and study the role in post chemotherapy treatment planning. This is an easily accessible, readily available, time efficient, cost-friendly modality which may prove useful in providing additional information in all new breast cancer patients, since MRI is performed only in a select group of patients. This may prove specifically helpful in patients with non-calcified masses and architectural distortion. In a recent study on DBT, cancers that manifested as architectural distortion at diagnosis included a higher percentage of invasive lobular carcinomas (20%) (11). It may also lead to better mass margin assessment, tumor size and presence of satellite lesions. It is also a useful tool in evaluating the contralateral breast, especially since breast MRI is not performed in every new breast cancer patient at our institution.

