2.0 Objectives

The primary aim of the study is to study the efficacy and additional role of digital breast tomosynthesis (DBT) for patients with a new diagnosis of breast cancer. In the current clinical practice at our institution, standard 2-dimensional (2-D) mammograms (DM) are performed as standard of care to evaluate the extent of disease in patients with new diagnosis of breast cancer. DBT (colloquially referred to as a 3-dimensional mammogram) is only occasionally performed, at the discretion of the breast radiologist to further evaluate the findings of the 2-D mammogram. Recently published data shows a greater efficacy of DBT with increased cancer detection and a reduced call back rate for screening mammography (1-4). Chudgar et al assessed MR extent of disease for cancers detected on DBT versus DM alone (5). Additional studies evaluated role of DBT in cancer detection and tumor size assessment in comparison to other diagnostic modalities (6-8), specifically Mariscotti et al assessed its role in characterizing invasive lobular cancers (9). Our hypothesis is that DBT may provide additional information to evaluate the extent of disease, including possible multifocality and multicentricity and additional findings including margin assessment and tumor size that would aid in staging a new breast cancer patient. This would impact surgical planning and improve patient outcomes. DBT is a relatively inexpensive test; in comparison to breast MRI which is the alternative study performed to evaluate extent of disease in selected new breast cancer patients. One of the reasons that a breast radiologist may recommend a breast MRI for a new breast cancer patient is if the patient has dense breast tissue on mammography. Performing DBT in these patients may improve the mammographic information about the extent of disease. Also, all the previously recently published studies were performed using different vendor versions of DBT other than Siemens used at our site.

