3.2 Number of Subjects

Approximately 150 subjects will be enrolled in this trial.

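### The MRI-versus-DBT comparison is planned as McNemar's test alone, so a non-significant result could not show whether the two exams find similar disease

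*Combined protocol and SAP*

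**What the plan says.** The plan for comparing MRI with DBT is one sentence in section 14.0: "McNemar's test will be used to compare the findings on MRI and DBT". It gives no paired difference, confidence interval, margin, power or expected number of women with MRI. It does not define a finding or say whether the unit is the woman, the breast or the lesion.

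Section 14.0 does plan an estimate with a 95% CI for the primary proportion (women whose surgical plan changes). It justifies the sample size by the width of that interval, which "can be constructed with width of +/- 8% or tighter with 150 patients". That statement does not cover the MRI comparison.

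On how many women will have MRI, section 1.1 says only that "Currently, only MRI is occasionally used to evaluate the extent of disease in some cancer patients", with selection "based on age, breast density and pathology subtype of the breast cancer". It later argues for DBT "since MRI is performed only in a select group of patients". Section 3.2 says that "Approximately 150 subjects will be enrolled in this trial", and section 3.0 does not require MRI.

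On how the two exams are related, section 1.1 says "Our goal is to evaluate the efficacy of DBT in a similar fashion to study its role in cancer extent evaluation", directly after describing the use of MRI. Section 2.0 says "DBT is a relatively inexpensive test; in comparison to breast MRI which is the alternative study performed to evaluate extent of disease".

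**The concern.** McNemar's test asks whether the two exams have equal marginal detection rates. If it is not significant, either the rates are close or there were too few discordant women to tell. The p-value does not separate these explanations and does not show how large a DBT deficit the data still allow.

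This matters because the background sets DBT beside MRI on cost and access. A reader of the results will want to know how much DBT misses or adds relative to MRI. The fewer women who have both exams, the more likely a non-significant result becomes for any given true difference. With no planned interval, the report need not show how imprecise the comparison is.

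**Working it through.** **1. The plan's own figure.** It concerns the primary proportion only. The Wald half-width at p = 0.5 and n = 150 is 1.96 × √(0.25/150) = 8.00 points. The stated ±8% is reproduced. The documents give no corresponding figure for MRI versus DBT.

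**2. Inputs for the MRI comparison.**
- From the documents: 150 women enrolled; MRI in a select subset; McNemar's test.
- Assumed, because the documents do not say: 30, 45, 60 or 75 women with both exams (20% to 50% of 150); two-sided 0.05 (section 14.0 does not say whether Holm's method covers this test); the exact version of the test; the woman as the unit; and the discordance rates below.

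**3. Minimum evidence for significance.** If all m discordant women fall in one direction, the exact two-sided p is 2 × 0.5^m. Five gives 0.0625 and six gives 0.031. At least six discordant women are therefore needed, whatever the total. With 30 pairs and a 20% discordance rate, the chance of five or fewer is 43%, and then significance is impossible.

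**4. Power and precision.** Let b be the proportion positive on MRI only and c the proportion positive on DBT only. Power is the sum, over the binomial number of discordant pairs, of the probability that the exact test gives p ≤ 0.05. The half-width of the 95% CI for the paired difference is 1.96 × √((b + c − (b − c)²)/n). At 15% versus 5% and n = 30 this is 1.96 × √((0.20 − 0.01)/30) = 15.6 points.

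| Pairs | Exact power, 15% vs 5% | Half-width, 15% vs 5% (points) | Exact power, 20% vs 5% | Exact power, 25% vs 5% |
|---|---|---|---|---|
| 30 | 10% | 15.6 | 24% | 40% |
| 45 | 21% | 12.7 | 42% | 64% |
| 60 | 31% | 11.0 | 58% | 80% |
| 75 | 41% | 9.9 | 71% | 89% |

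With the uncorrected chi-square version of the test, power at 15% versus 5% is 22%, 30%, 40% and 50%.

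**5. Upper bound.** If all 150 women had MRI, exact power at 15% versus 5% would be 75% and the half-width 1.96 × √(0.19/150) = 7.0 points.

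**6. Two possible results with 30 pairs.** Wald intervals are used here for simplicity.
- MRI-only 5, DBT-only 1: difference 4/30 = 13 points, standard error √(6 − 16/30)/30 = 0.078, 95% CI −2 to 29 points, exact p = 0.22.
- MRI-only 2, DBT-only 2: difference 0, standard error √4/30 = 0.067, 95% CI −13 to 13 points, exact p = 1.0.

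Both are non-significant. The intervals show that neither establishes similarity, and that the first allows an MRI advantage of up to 29 points.

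**The case against.** The strongest reply is that the protocol never claims that DBT matches or could replace MRI. The primary objective (section 2.1) is how often DBT changes the surgical plan. The objectives in section 2.2, which the Protocol Summary lists as exploratory, concern atypical findings, 2D predictors, and work-up with false positives. None mentions MRI. The design in section 3.0 compares DBT with the standard mammographic work-up. Much of section 1.1 presents DBT as useful for all new patients because many never have MRI. That is a gap-filling argument more than a substitution argument. All of this stands. A reader might infer from the cost comparison in section 2.0 that the trial aims to show DBT is as good as MRI, but the documents state no equivalence or non-inferiority hypothesis and no margin.

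The subset size is also unknown. The words used for MRI suggest a minority, but no number is given, so a small subset is an inference. Nor do the documents support saying that non-significance is the likely result even when MRI clearly finds more. At 25% versus 5%, exact power is already 64% with 45 pairs and 89% with 75. The less conservative chi-square version gives higher power at 15% versus 5%.

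Finally, McNemar's test is a standard test for paired binary data, and an interval can be computed from the same table afterwards. That is true, but prespecifying the interval ensures it is reported whatever the p-value. The point also does not depend on a small subset, because non-significance is not evidence of similarity at any n.

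**Conclusion.** The point holds in a limited form. Section 14.0 commits to an MRI-versus-DBT comparison and plans only a p-value for it. The number of pairs is not fixed by the design and is probably well below 150. A non-significant result would therefore leave open how much DBT misses relative to MRI.

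The size depends on assumptions. With 30 to 75 pairs, exact power is 10% to 41% at 15% versus 5% and 40% to 89% at 25% versus 5%. At 15% versus 5% the difference would be known only to within about 16 to 10 points.

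This is a cheap improvement to an ancillary analysis. It does not affect the primary estimate, its interval or the sample size. A reader might go further and infer that the trial fails a stated equivalence aim, or that it will probably miss a clear MRI advantage. The first is unsupported because no such aim is stated, and the second because the documents give neither the number with MRI nor the detection rates.

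**What to change.** Replace the McNemar sentence in section 14.0 with:

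> Among women with both exams, the MRI-minus-DBT difference in the proportion of women with an additional finding will be reported with a 95% CI for paired proportions (Tango or Newcombe) and both discordant counts. The McNemar p-value is supplementary. The comparison is descriptive and limited to women selected for MRI, and non-significance will not be read as equivalence.

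The same edit should define an additional finding, including whether it must be confirmed by pathology. It should also add MRI findings to the data list in section 3.0, where they do not appear. Without a definition, the interval would not show what DBT misses.

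The cost is a short change to the text. It needs no extra patients or imaging, because the interval uses the same paired table as McNemar's test. The downside is that the interval may be wide and will show that the comparison is imprecise.
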